9.0 Ancillary Treatment/Supportive Care

- **9.1** Antiemetics may be used at the discretion of the attending physician.
- **9.2** Radiation therapy for symptom palliation is allowed. Radiation should be to non-target sites (i.e. painful pre-existing bony metastasis) in patients who are benefiting from therapy.
- **9.3** Corticosteroids for treatment of adrenal insufficiency or severe nausea and vomiting are permitted.
- 9.4 Blood products should be utilized as clinically warranted and following institutional policies and recommendations. The use of growth factors is not permitted during study treatment.

- 9.5 Patients should receive full supportive care while on this study. This includes blood product support, antibiotic treatment, and treatment of other newly diagnosed or concurrent medical conditions. All blood products and concomitant medications such as antidiarrheals, analgesics, and/or antiemetics received from the first day of study treatment administration until 30 days after the final dose will be recorded in the medical records.
- **9.6** Bisphosphonates: Patients with lytic metastatic bone disease may receive bisphosphonates at the discretion of the treating physician.
- **9.7** Rash: The use of corticosteroid creams, and/or antihistamines are allowed at physician discretion.
- 9.8 Diarrhea: This could be managed conservatively with loperamide. The recommended dose of loperamide is 4 mg at first onset, followed by 2 mg every 2-4 hours until diarrhea free (maximum 16 mg/day).

In the event of grade 3 or 4 diarrhea, the following supportive measures are allowed: hydration, octreotide, and antidiarrheals.

If diarrhea is severe (requiring intravenous rehydration) and/or associated with fever or severe neutropenia (grade 3 or 4), broad-spectrum antibiotics must be prescribed. Patients with severe diarrhea or any diarrhea associated with severe nausea or vomiting **should be hospitalized** for intravenous hydration and correction of electrolyte imbalances.

10.0 Adverse Event (AE) Reporting and Monitoring

10.1 Adverse Event Characteristics

CTCAE term (AE description) and grade: The descriptions and grading scales found in the revised NCI Common Terminology Criteria for Adverse Events (CTCAE) version 4.0 will be utilized for AE reporting. All appropriate treatment areas should have access to a copy of the CTCAE version 4.0. A copy of the CTCAE version 4.0 can be downloaded from the CTEP web site (http://ctep.cancer.gov/forms/default.htm).

10.11 Adverse event monitoring and reporting is a routine part of every clinical trial. First, identify and grade the severity of the event using the CTCAE v4.0. Next, determine whether the event is expected or unexpected (refer to Sections 10.12 and 15.0) and if the adverse event is related to the medical treatment or procedure (see Section 10.13). With this information, determine whether an adverse event should be reported to the NCI as an expedited report (see Section 10.2) or as part of the routinely reported clinical data. Important: All AEs reported via

expedited mechanisms must also be reported via the routine data reporting mechanisms defined by the protocol (see Section 10.3 and 18.0).

Expedited and/or routine reports are to be completed within the timeframes and via the mechanisms specified in Sections 10.2 and 10.3. All expedited AE reports must also be sent to the local Institutional Review Board (IRB) according to local IRB's policies and procedures.

10.12 Expected vs. Unexpected

- The determination of whether an AE is expected is based on agentspecific adverse event information provided in Section 15.0 of the protocol.
- Unexpected AEs are those not listed in the agent-specific adverse event information provided in Section 15.0 of the protocol.

10.13 Assessment of Attribution

When assessing whether an adverse event is related to a medical treatment or procedure, the following attribution categories are utilized:

Definite - The adverse event *is clearly related* to the investigational agent(s). Probable - The adverse event *is likely related* to the investigational agent(s).

Possible - The adverse event *may be related* to the investigational agent(s).

Unlikely - The adverse event *is doubtfully related* to the investigational agent(s).

Unrelated - The adverse event *is clearly NOT related* to the investigational agent(s)

10.2 Expedited Adverse Event Reporting Requirements

10.21 Paper reporting will be done via the AdEERS form found at Adverse Event Expedited Report – Single Agent or Multiple Agents

| | Grade 4 or 5 ¹ Unexpected/ Expected Regardless of Attribution | Grade 3 Unexpected/ Expected Regardless of Attribution | Other Grade 4 or 5 Events and/or any Hospitalization During Treatment Not Otherwise Warranting an Expedited Report |
|---|--|--|--|
| Submit written report within 5 working days ² | X | X | |
| Submit Grade 4 or 5 Non-AER Reportable Events/Hospitalization in EDC within 5 working days. ³ | | | X^3 |

- 1. Includes all deaths within 30 days of the last dose of agent regardless of attribution or any death attributed to the agent(s) (possible, probable, or definite) regardless of timeframe.
- 2. Use paper *Adverse Event Expedited Report Single Agent or Multiple Agents* report available within the study forms packet

.

Mayo Clinic Cancer Center (MCCC) Institutions: Provide copies, along with the UPIRTSO cover sheet, by [contact]) to the MCCC Regulatory Affairs Unit (RAU) Risk Information Specialist who will determine and complete IRB reporting. The RAU will submit to the MCCC SAE Coordinator and the MCCC IND Coordinator to determine if FDA submission is needed.

3. Complete a Notification Form: Grade 4 or 5 Non-AER Reportable Events/Hospitalization Form electronically via the Data Entry System within 5 working days of the date the clinical research associate (CRA) is aware of the event(s) necessitating the form. If expedited written report was submitted, this form does not need to be completed.

10.3 Adverse events to be graded at each evaluation and pretreatment symptoms/conditions to be evaluated at baseline per the CTCAE v4.0 grading unless otherwise stated in the table below:

| System Organ Class (SOC) | Adverse event/Symptoms | Baseline | Each evaluation |
|--|----------------------------|----------|-----------------|
| General disorders and administration site conditions | Fever | X | X |
| Blood and lymphatics system disorders | Anemia | X | X |
| Investigations | Neutrophil count decreased | X | X |
| | Platelet count decreased | X | X |
| | Creatinine increased | X | X |
| | | X | X |
| | Cholesterol high | X | X |
| | Blood bilirubin increased | | |
| Vascular disorders | Hypotension | X | X |
| | Flushing | X | X |
| Skin and Subcutaneous tissue orders | Rash Acneiform | X | X |
| Gastrointestinal disorders | # of stools | X | |
| | Diarrhea | | X |
| | Nausea | X | X |
| | Vomiting | X | X |
| | Mucositis, oral | X | X |

| Infections and | Bladder Infection | X | X |
|-----------------------------------|----------------------|---|---|
| Infestations | Bronchial Infection | X | X |
| | Skin Infection | X | X |
| | Lung Infection | X | X |
| Renal and urinary disorders | Proteinuria | X | X |
| Metabolism and | Hyperglycemia | X | X |
| Nutrition disorders | Hypertriglyceridemia | X | X |
| Musculoskeletal | Myalgia | X | X |
| and connective tissue disorders | Arthralgia | X | X |
| Nervous system disorders | Dizziness | X | Х |
| Immune system disorders | Allergic Reaction | X | X |

- 10.31 Submit via appropriate MCCC Case Report Forms (i.e., paper or electronic, as applicable) the following AEs experienced by a patient and not specified in Section 10.3:
 - 10.311 Grade 2 AEs deemed *possibly, probably, or definitely* related to the study treatment or procedure.
 - 10.312 Grade 3 and 4 AEs regardless of attribution to the study treatment or procedure.
 - 10.313 Grade 5 AEs (Deaths)
 - 10.3131 Any death within 30 days of the patient's last study treatment or procedure regardless of attribution to the study treatment or procedure.

- 10.3132 Any death more than 30 days after the patient's last study treatment or procedure that is felt to be at least possibly treatment related must also be submitted as a Grade 5 AE, with a CTCAE type and attribution assigned.
- 10.32 Refer to the instructions in the Forms Packet (or electronic data entry screens, as applicable) regarding the submission of late occurring AEs following completion of the Active Monitoring Phase (i.e., compliance with Test Schedule in Section 4.0).

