8.2 Dose modification Table

| ☐ ☐ Use the NCI Common Terminology Criteria for Adverse Events (CTCAE) version | | | |
|--|---------------|-------|--------|
| 4.0* unless otherwise specified \square | | | |
| CTCAE System/Organ/ Class (SOC) | ADVERSE EVENT | AGENT | ACTION |
| BASED ON INTERVAL ADVERSE EVENT | | | |

| □ □ Use the N | CI Common Terminolog 4.0* unless o | | or Adverse Events (CTCAE) version |
|--|--|------------------------|---|
| CTCAE System/Organ/ Class (SOC) | ADVERSE EVENT | AGENT | ACTION |
| Investigations | Neutrophil count decreased Grade 4 Platelet count decreased Grade 4 | Auranofin Sirolimus | Delay therapy until ANC ≥ 1500 and/or PLT ≥ 100,000, and decrease by 1 dose level; discontinue treatment if toxicity persists beyond 14 days or if subject is already at dose level -2 and go to event monitoring phase per Section 18. |
| | Neutrophil count decreased Grade 3 Platelet count decreased Grade 3 | | Delay therapy until ANC ≥ 1500 and/or PLT ≥ 100,000. If delay is 1 week or less, resume at prior dose. If delay exceeds 7 days but is not more than 14 days, decrease by 1 dose level; discontinue treatment if toxicity persists beyond 14 days or if subject is already at dose level -2 and go to event monitoring phase per Section 18. |
| | Cholesterol High Grade 2 | | Institute appropriate lipid/cholesterol lowering therapy. Hold treatment until levels return to Grade 1. If unresolved by four weeks, discontinue auranofin and sirolimus therapy and go to event monitoring. |
| | Grade 3-4 | | Discontinue auranofin and sirolimus and go to event monitoring. |
| Respiratory, thoracic and mediastinal disorders | Interstitial pneumonitis any grade | Auranofin Sirolimus | Discontinue and go to event monitoring |

| \Box Use the NCI Common Terminology Criteria for Adverse Events (CTCAE) version 4.0* unless otherwise specified \Box \Box | | | |
|---|---------------------------------|------------------------|---|
| CTCAE System/Organ/ Class (SOC) | ADVERSE EVENT | AGENT | ACTION |
| Metabolism and nutrition disorders | Hypertriglyceridemia Grade 2 | Auranofin Sirolimus | Institute appropriate lipid/cholesterol lowering therapy. Hold treatment until levels return to Grade 1. If unresolved by four weeks, discontinue auranofin and sirolimus therapy and go to event monitoring. |
| | Grade 3-4 | | Discontinue auranofin and sirolimus and go to event monitoring. |

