14.0 Body Fluid Biospecimens: None

15.0 Drug Information

15.1 Auranofin for Oral Administration (Ridaura®)

- 15.11 **Background**: Auranofin is a gold compound which has antiinflammatory effects. Gold compounds can alter the immune response and have been shown to inhibit prostaglandin synthesis.
- 15.12 **Formulation**: Commercially available for oral administration as: Capsules: 3 mg [gold 29%]

- 15.13 **Preparation, storage, and stability**: Refer to package insert for complete preparation and dispensing instructions. Store oral tablets at room temperature. Dispense in a tight, light-resistant container.
- 15.14 **Administration:** Refer to the treatment section for specific administration instructions.

15.15 Pharmacokinetic information:

Absorption: ~25% of the gold in a dose of Auranofin is absorbed from the gastrointestinal tract

Protein binding: Moderate. In blood, approximately 60% of the gold is bound to plasma proteins; the remainder is present in red blood cells

Metabolism: Rapidly metabolized (the intact molecule has not been detected in blood)

Half-life elimination: Blood: 21 - 31 days. Tissue: 42 - 128 days **Excretion**: 60% of the absorbed gold (15% of the administered dose) is excreted in the urine; the remainder of the dose is excreted in the feces

15.16 Potential Drug Interactions:

In a single patient-report, there is the suggestion that concurrent administration of Auranofin and phenytoin may have increased phenytoin blood levels.

15.17 **Known potential adverse events:** Consult the package insert for the most current and complete information. Auranofin is contraindicated in patients with a history of any gold-induced disorders: anaphylactic reactions, necrotizing enterocolitis, pulmonary fibrosis, exfoliative dermatitis, bone marrow aplasia or other severe hematologic disorders.

Common known potential toxicities, > 10%:

Dermatologic: Dermatitis (aggravated by sunlight), pruritus, actinic rash, hair loss, urticaria

Gastrointestinal: Nausea, vomiting, abdominal cramps, diarrhea, loose stools, constipation, dysgeusia, stomatitis, glossitis Hematologic: Anemia, leukopenia, thrombocytopenia, Eosinophilia

Hepatic: Elevated liver enzymes

Renal: Hematuria

Less common known potential toxicities, 1% - 10%:

Gastrointestinal: Anorexia, flatulence, dyspepsia

Ocular: Conjunctivitis Renal: Proteinuria

Rare known potential toxicities, <1% (Limited to important or life-threatening):

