Dermatologic: Generalized exfoliative dermatitis, angioedema

Gastrointestinal: Dysphagia, gastrointestinal bleeding,

melena, positive stool for occult blood, ulcerative enterocolitis

Mucous membrane: Gingivitis

Hematologic: Aplastic anemia, neutropenia, agranulocytosis, pure

red cell aplasia, pancytopenia

Hepatic: Jaundice

Neurologic: Peripheral neuropathy Respiratory: Interstitial pneumonitis

15.18 Drug procurement:

Commercial supplies. Pharmacies or clinics shall obtain supplies from normal commercial supply chain or wholesaler.

15.19 Nursing Guidelines:

- 15.191 Auranofin is contraindicated in patients with history of gold-induced disorders (see section 15.17). Assess patients for any of these conditions, hold drug and notify study team.
- 15.192 Dermatitis is common and is exacerbated by sunlight. Instruct patients to avoid prolonged sun exposure without protection (i.e sunscreen SPF 30+ and covering up with clothing).
- 15.193 Patients may experience hair loss. Warn patients of this possibility.
- 15.194 Gastrointestinal side effects are common (diarrhea, constipation, nausea, vomiting, etc.) Treat symptomatically and assess for effectiveness.
- 15.195 Monitor LFT's as elevated liver enzymes have been seen. Report elevations to study physician.
- 15.196 Cytopenias can be seen. Rarely these can be serious. Monitor CBC w/differential. Instruct patients to report any excessive bruising or bleeding and/or signs/symptoms of infection to study team.
- 15.197 Instruct patients to report any hematuria to the study team.
- 15.198 Pneumonitis has been reported rarely, but can be serious and life-threatening. Instruct patients to report any cough, shortness of breath, and/or chest pain to the study team immediately.

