Increased Effect/Toxicity: Cyclosporine may increase Sirolimus concentrations during concurrent therapy; Sirolimus should be taken 4 hours after cyclosporine oral solution (modified) and/or cyclosporine capsules (modified). CYP3A4 inhibitors may increase the levels/effects of Sirolimus. Refer to package insert for a list of CYP3A4 inhibitors.

Concurrent use of ACE inhibitors may increase the risk of angioedema. Concurrent live organism vaccines may increase the adverse/toxic effect of the vaccine; vaccinial infections are possible (avoid concurrent use).

Voriconazole may decrease the metabolism (via CYP isoenzymes) of Sirolimus (avoid concurrent use). Concurrent therapy with calcineurin inhibitors (cyclosporine, tacrolimus) may increase the risk of HUS/TTP/TMA.

Decreased Effect: CYP3A4 inducers may decrease the levels/effects of Sirolimus. Vaccination (dead organisms) may be less effective with concurrent sirolimus (monitor).

Ethanol/Nutrition/Herb Interactions:

Food: Do not administer with grapefruit juice; may decrease clearance of sirolimus. Ingestion with high-fat meals decreases peak concentrations but

increases AUC by 23% to 35%. Sirolimus should be taken consistently either with or without food to minimize variability.

15.27 **Known potential adverse events:** Consult the package insert for the most current and complete information.

Common or severe toxicity: Hypertension, edema, capillary leak syndrome, poor wound healing, hypertriglyceridemia, hypercholesterolemia, hypokalemia, constipation, diarrhea, dyspepsia, nausea and vomiting, deep venous and arterial thrombosis, abnormal liver function tests, hypersensitivity reaction, infection, sepsis, lymphoma, arthralgia, headache, renal failure, interstitial pneumonitis, pulmonary hemorrhage, thrombocytopenia and leukopenia.

15.28 **Drug procurement:** Commercial supplies. Pharmacies or clinics shall obtain supplies from normal commercial supply chain or wholesaler.

15.29 Nursing Guidelines:

15.291 Patients should be instructed that tablets should be swallowed whole, and not crush, split or chewed. If solution is used, it should be mixed with at least 2 ounces of water or orange juice. No other liquids should be used for dilution. Mixed solution should be drunk immediately, then add an additional 4 ounces of water or juice to the cup, stir vigorously and again drunk immediately.

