- 15.292 Patients should not receive vaccination with live vaccination preparations while on study medication. Patients should be instructed to check with the study team prior to receiving any vaccine.
- 15.293 Hypertension is a known side effect. Monitor patients BP as outlined in the protocol or as symptoms dictate.
- 15.294 Elevated lipid levels, specifically triglycerides can be seen. Monitor lipid levels as outlined in the protocol.55 MC1111
- 15.295 Thrombosis (venous and arterial) can be seen. Instruct patient in the warning signs of this and to seek out proper medical treatment.
- 15.296 Cytopenias (thrombocytopenia/leukopenia) can be a side effect of agent. Instruct patient in signs and symptoms of infection and to report any unusual bruising or bleeding to the study team.
- 15.297 Infection (including sepsis) and delayed wound healing are possible. Instruct patients to check with the study team prior to having any invasive procedure done. Instruct patients to report any fever or infection symptoms to the study team immediately.
- 15.298 Pneumonitis is seen with this agent. Instruct patients to report any cough or shortness of breath to the team.
- 15.299a Headache is a known side effect. Administer analgesics as ordered and assess for their effectiveness.
- 15.299b GI disturbances are common and vary (diarrhea, constipation, nausea,

vomiting, dyspepsia). Treat symptomatically and assess for effectiveness.

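### The 10.3 list of routinely graded adverse events omits several toxicities that Sections 7.213, 8.2 and 15 treat as important, so their low grades and baseline grades are not required data

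*Combined protocol and SAP*

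**What the plan says.** **The routine list.** Section 10.3 names the events to be graded under CTCAE v4.0 at baseline and at each evaluation. Its vascular block reads "Vascular disorders | Hypotension | X | X", followed by flushing. The only rash row is acneiform rash, the only renal and urinary row is proteinuria, and the only liver-related row is bilirubin.

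**The expected toxicities.** The sirolimus list in 15.27 opens with "Common or severe toxicity: Hypertension, edema, capillary leak syndrome, poor wound healing" and ends with "renal failure, interstitial pneumonitis, pulmonary hemorrhage, thrombocytopenia and leukopenia". For auranofin, 15.17 places "Renal: Hematuria", "Hepatic: Elevated liver enzymes", dermatitis and pruritus in the group above 10%, and "Respiratory: Interstitial pneumonitis" in the group below 1%.

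**The action rules.** The table in 8.2 stops both drugs for "Interstitial pneumonitis any grade". The table in 7.213 makes hematuria of Grade 3 or higher a DLT.

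**Events outside the list.** Under 10.31, an event not named in 10.3 goes on the case report form if it is Grade 2 and at least possibly related, Grade 3 or 4 whatever the attribution, or a Grade 5 event as defined there. Section 10.2 adds expedited reports for Grades 3 to 5. Section 6.38 requires baseline grading by reference to 10.3.

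**The analyses.** For phase I, 16.21 promises the number and severity of every adverse event. The adverse-event paragraph of 16.52 uses each patient's maximum grade for each event type.

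**Blood pressure.** The sirolimus nursing guideline 15.293 says "Monitor patients BP as outlined in the protocol or as symptoms dictate".

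**The concern.** Secondary goal 2.22 is the adverse-event profile of a two-drug combination, and 10.3 is the main instrument for it. An event on that list is graded at every evaluation and has a baseline grade. An event off the list is recorded only above a threshold and has no required baseline grade.

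The list does not follow the protocol's own account of what to expect. It includes hypotension and flushing, which neither 15.17 nor 15.27 names, and leaves out several toxicities that those sections do name. At stake is whether the final tables can show low grades of these toxicities and separate them from conditions present at entry. Entry conditions matter here. Section 3.15 admits AST and ALT above the upper limit of normal, with a wider limit if the liver is involved. Section 3.26 excludes hypertension when severe or uncontrolled, and interstitial fibrosis when extensive and symptomatic, so milder forms can be present at registration.

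**Working it through.** The plan gives no figure to reproduce, so the check compares sections and counts categories.

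**Step 1. Compare the lists.**

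| Toxicity | Section 15 | Action rule | Row in 10.3 |
|---|---|---|---|
| Hypertension | 15.27, first item | none specific | none |
| Interstitial pneumonitis | 15.27; 15.17 (<1%) | 8.2, any grade | none |
| Hematuria | 15.17 (>10%) | 7.213, Grade 3 or higher | none |
| Liver enzymes (AST/ALT) | 15.17 (>10%) | none specific | none (bilirubin only) |
| Dermatitis, pruritus | 15.17 (>10%) | none specific | acneiform rash only |

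One Investigations row in 10.3 appears without a name in the extracted text. That block has five named terms and five marked rows, so this is a shift in the table and not a concealed AST/ALT row.

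**Step 2. Compare 10.3 with the action rules.** Section 8.2 names five specific events: neutrophils, platelets, cholesterol, triglycerides and interstitial pneumonitis. Four have a row in 10.3. Pneumonitis, the only one for which every grade ends treatment, does not. Section 7.213 names eight DLT items. If the allergic-reaction row is taken to cover anaphylaxis, seven have a row and hematuria does not.

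**Step 3. Count what 10.31 collects for an unlisted term.** Cross five grades with two attributions (at least possibly related, or not): 5 × 2 = 10 categories.

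- Grade 2: related only, 1.
- Grade 3: both, 2.
- Grade 4: both, 2.
- Grade 5: both, 2 (unrelated deaths only if within 30 days of last treatment or procedure).
- Collected: 1 + 2 + 2 + 2 = 7.
- Not required: 10 − 7 = 3, namely Grade 1 related, Grade 1 unrelated and Grade 2 unrelated.

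These are categories, not frequencies.

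**Step 4. Apply this to each use of the data.**

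- DLT hematuria needs Grade 3 or higher, so every such case is collected.
- The stopping rule in 16.532 needs a related non-hematologic event of Grade 4 or higher, so every such case is collected.
- Pneumonitis under 8.2 acts at any grade. In the three uncollected categories treatment ends, yet no graded adverse-event record is required.
- The 16.21 table and the maximum grade in 16.52 need all grades. For the terms in Step 1 the low grades are not systematically available.

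**Step 5. Check blood pressure.** Section 4.0 has a row for history, examination, weight and performance status, but no row names blood pressure. The first half of the 15.293 instruction therefore refers to nothing explicit.

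**The case against.** The strongest reply is that this is a deliberate two-tier design: a short routine list with a threshold for everything else. No section says that 10.3 must mirror Section 15, which 10.12 uses only to decide whether an event is expected. This stands as far as it goes. It does not explain why an event that ends treatment at any grade is off the routine list, or how 16.21 can report every event.

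A reader might infer more than the documents support, in five ways.

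- *That the safety profile as a whole is under-counted.* It is not. Sections 10.31 and 10.2 capture the clinically important grades.
- *That the regimen will look safer than it is.* The direction is not established. Missing Grade 1 events lower the counts, but without a baseline grade a pre-existing abnormality may be counted as an on-treatment event, which raises them.
- *That a rise in AST/ALT on treatment cannot be told from an earlier one.* Section 4.0 requires AST/ALT and urinalysis before registration, weekly in cycle 1 and before later cycles, so the values exist at the site. What is missing is a required grade. Section 18 names no separate laboratory form, so the documents do not show whether the values reach the database.
- *That about four patients per toxicity are missed, from 0.10 × 41 = 4.1.* That product is the expected number with the toxicity at any grade, at the lower bound of the above-10% group. The 41 is also an accrual target that allows for cancellations, ineligibility and violations. The documents give no grade distribution, so the missed share could lie anywhere between none and all.
- *That hypotension and flushing are errors to be removed.* They are plausible signs of reactions the protocol does name, such as anaphylaxis and capillary leak syndrome, and both drug lists defer to the package insert for completeness.

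Two further replies have partial force. Section 15.293 also allows monitoring when symptoms call for it, so it can be followed without a row in Section 4.0. A pneumonitis discontinuation would also leave a trace on the treatment and end-of-treatment forms required in Section 18, though their content is not shown and the plan does not say that they carry a CTCAE grade and attribution.

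**Conclusion.** The point holds as a gap in low-grade and baseline recording. For hypertension, interstitial pneumonitis, hematuria, AST/ALT increase and non-acneiform rash or pruritus, Grade 1 and unrelated Grade 2 events are not required on the case report form, and no baseline grade is required. The clearest internal mismatch is pneumonitis: 8.2 acts on any grade, while 10.3 and 10.31 leave three of the ten categories without a required record. The tables in 16.21 and 16.52 will be incomplete at low grades for toxicities the protocol itself expects.

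Related Grade 2 events, Grade 3-5 events as 10.31 defines them, the DLT count and the stopping rule are not affected. Neither the number of missed events nor the direction of any bias can be derived from the documents. This is a worthwhile, inexpensive improvement and not a threat to the trial's main conclusions.

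The conclusion assumes that the adverse-event forms follow 10.3 and 10.31 and carry no extra preprinted terms. The forms are not part of the documents. Sites may record more than is required, but the plan does not oblige them to.

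**What to change.** Add rows to 10.3 for hypertension, pneumonitis, hematuria, ALT increased, AST increased and a general rash/pruritus term, each graded at baseline and at each evaluation. Keep every existing row. Because 6.38 refers to 10.3, the baseline requirement then follows without further edits.

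Reconcile 15.293 with Section 4.0, so that the reference to blood-pressure monitoring points to a stated entry or is reworded.

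No dose, stopping or treatment rule needs to change for this. AST/ALT and urinalysis are already in the test schedule. The cost is an edit to one table and a few more lines on each adverse-event form.
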